## **7.4. Details of Procedures and Evaluations**

### **7.4.1. Medical History, Physical Exam, Physical Measurements**

A Medical History will be obtained at screening to ensure subject meets all inclusion and exclusion criteria. If the subject consents to be enrolled in the study, a detailed medical history will be obtained at the baseline visit. Please include in history any toxicities related to previous treatments, if applicable.

Physical examinations including weight measurement will be performed at the time points outlined in Table 3.

#### **7.4.1.1. Vital Signs**

Vital signs consist of blood pressure, heart rate, respiratory rate and temperature measurements. Vital signs will be obtained as outlined in Table 3.

#### **7.4.1.2. Pregnancy Testing**

WOCBP are required to have several pregnancy tests performed. A negative serum pregnancy test must be documented at the screening visit. Additionally WOCBP must exhibit a *negative serum or urine pregnancy test* (minimum sensitivity 25 IU/L or equivalent units of HCG) *prior to the start of each cycle of study drug*.

#### **7.4.1.3. ECOG Status**

ECOG performance status will be evaluated at the screening evaluation and at each visit.

#### **7.3.1.4. Laboratory Test Assessments**

Results of all safety laboratory collections must be obtained and reviewed in advance of study drug dosing, as applicable.

During both Treatment and Follow-up Phases, labs must be collected in the following timeframes:

- Required laboratory examinations must be collected within 7 days prior to dosing. Screening labs can be used to satisfy the C1D1 requirements if collected within 7 days of first treatment.

## **7.5. Research Sample Collection**

For those subjects who agree to have the research samples collected, the following will be collected:

- Serum and PBMC will be collected at baseline or on C1D1 prior to treatment, every 3 months during nivolumab therapy, and then every 6 months thereafter through follow up Month 24.
- CTCs will be collected at baseline or on C1D1 prior to treatment, 3 months, and 12 months.

Additional laboratory testing thereafter will be performed at the discretion of the investigator.

At EACH time point please submit the following:

- 2 - 10 ml GREEN top tubes
- 4 - 10 ml LAVENDER top EDTA tubes
- 2 - 10 ml RED top (glass) tube

Each tube must be clearly labeled to include:

- Protocol number
- Patient sequence number
- Patient initials

- Originating institution/investigator name
- Date and time drawn
- Collection time point

See laboratory manual for additional information.

## **8. EVALUATION OF SAFETY**

### **8.1. Data and Safety Monitoring Plan**

A data safety monitoring plan for this study consists of monitoring the adverse events and data to evaluate the efficacy and effectiveness of the study. The SKCC DSMC will assign a medical monitor to the study who will be responsible for the day-to-day monitoring of all AEs and SAEs reported from the trial. The medical monitor will be responsible to review these at quarterly DSMC meetings and as needed. Decisions to continue or close the trial to accrual and subject recruitment, accrual and retention, and/or if the trial should continue are also discussed during these meetings. Any modifications necessary to ensure subject safety are discussed and modifications will be submitted to the IRB. If any literature becomes available which suggests that conducting this trial is no longer ethical, the study will be terminated and the IRB will be notified of the new findings. The IRB will be notified of any change in the risk/benefit ratio that would affect whether the study should continue. All serious adverse events will be reported to the IRB according to the established guidelines. A cumulative summary of all events occurring during this study will also be submitted to the IRB with the annual renewal report. Serious adverse events will also be reported to the sponsor and /or other regulatory agency as per their requirements.

### **8.2. Specification of Safety Parameters**

#### **8.2.1. Unanticipated Problems**

Unanticipated problems (UAPs) include, in general, any incident, experience, or outcome that meets the following criteria:

- Unexpected in terms of nature, severity, or frequency given (a) the research procedures that are described in the protocol-related documents, such as the IRB-approved research protocol and informed consent document; and (b) the characteristics of the participant population being studied;

UAPs are considered to pose risk to participants or others when they suggest that the research places participants or others at a greater risk of harm (including physical, psychological, economic, or social harm) than was previously known or recognized.

#### **8.2.2. Adverse Events**

An adverse event is any untoward or unfavorable medical occurrence or worsening of a pre-existing medical condition in a clinical investigation participant, including any abnormal sign (for example, abnormal physical exam or laboratory finding), symptom, or disease, temporally associated with the participant's participation in the research, whether or not considered related to the participant's participation in the research.

#### **8.2.3. Serious Adverse Events**

A serious adverse event (SAE) is one that meets one or more of the following criteria:

- Results in death
- Is life-threatening (places the participant at immediate risk of death from the event as it

occurred)

- Is disabling or incapacitating
- Results in inpatient hospitalization or prolongation of existing hospitalization
- Results in a persistent or significant disability or incapacity
- Results in a congenital anomaly or birth defect
- An important medical event that may not result in death, be life threatening, or require hospitalization may be considered an SAE when, based upon appropriate medical judgment, the event may jeopardize the participant or may require intervention to prevent one of the outcomes listed in this definition.

The following hospitalizations are not considered SAEs in BMS clinical studies:

- A visit to the emergency room or other hospital department < 24 hours, that does not result in admission (unless considered an important medical or life-threatening event)
- Elective surgery, planned prior to signing consent
- Admissions as per protocol for a planned medical/surgical procedure
- Routine health assessment requiring admission for baseline/trending of health status (eg, routine colonoscopy)
- Medical/surgical admission other than to remedy ill health and planned prior to entry into the study. Appropriate documentation is required in these cases.
- Admission encountered for another life circumstance that carries no bearing on health status and requires no medical/surgical intervention (eg, lack of housing, economic inadequacy, caregiver respite, family circumstances, administrative reason).
- Admission for administration of anticancer therapy in the absence of any other SAEs (applies to oncology protocols)

### **8.3. Safety Assessment and Follow-Up**

Adverse event reporting will begin after study treatment, unless AE/SAE is caused by a study specific screening procedure, and continue until 30 days after the last dose of study treatment. At each study visit, the investigator (or designee) will inquire about the occurrence of AE/SAEs since the last visit. Events will be followed for outcome information until resolution or stabilization.

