### **5.7. Procedures for Subjects Exhibiting Immune-Related Adverse Events**

Immune-related AEs may be defined as an AE of unknown etiology, associated with drug exposure and consistent with an immune phenomenon. Immune-related AEs may be predicted based on the nature of the nivolumab compound, its mechanism of action, and reported experience with immunotherapies that have a similar mechanism of action. Special attention must be paid to AEs that may be suggestive of potential irAEs. An irAE can occur shortly after the first dose or several months after the last dose of treatment.

[figure not shown]
Recommendations for management of specific immune-mediated AEs such as pneumonitis, enterocolitis, hepatitis, dermatitis, neuropathies, endocrinopathies, and other immune-mediated AEs are detailed in the sections below.

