## **6. STUDY SCHEDULE**

### **6.1. Time and Events Schedule**

**Table 3.** Time and Events Schedule is on the following page.

	Screening	Treatment Cycle (4 Week Cycle) a												Follow up (months) k										End of Treatment (EOT)/Withdrawal m
														M1 Post-Scans	Every 3 months from last Infusion x 1 year				Every 6 months subsequently x2 years				Final Year	
															M3	M6	M9	M12	M18	M24	M30	M36	M42 and M48	
	28 Days*	1	2	3	4	5	6	7	8	9	10	11	12		M3	M6	M9	M12	M18	M24	M30	M36	M42 and M48	
Informed Consent	X																							
History and Physical Exam b	X	X	X	X	X	X	X	X	X	X	X	X	X	x	X	X	X	X	X	X	X	X	X	X
Vital Signs	X	X	X	X	X	X	X	X	X	X	X	X	X	X	X	X	X	X	X	X	X	X	X	X
Beta HCG Pregnancy Test c	X	X	X	X	X	X	X	X	X	X	X	X	X											
ECOG Performance Status	X	X	X	X	X	X	X	X	X	X	X	X	X	X	X	X	X	X	X	X	X	X	X	X
Laboratory Assessments d	X	X	X	X	X	X	X	X	X	X	X	X	X	X	X	X	X	X	X	X	X	X	X	X
Cross-sectional imaging, including at minimum chest, abdomen and pelvis e	X							X						X		X		X	X	X	X	X	X	X l
AE Assessment		Assessed at every visit																						
Research blood sample collection f	X j	X j			X			X			X			X		X		X	X	X				X
CTC Analysis g	X j	X j			X									X										
Quality of Life Assessment (Appendix #1)		X	X	X	X	X	X	X	X	X	X	X	X			X		X	X	X	X	X	X	X
Nivolumab Therapy		X	X	X	X	X	X	X	X	X	X	X	X											
Archived tissue request	X																							

\*Screening period is a total of 28 days; Screening labs that are performed within 7 days prior to C1D1 do not need to be repeated

a. Treatment may be administered with a window of ± 7 days.

b. Visits may be performed with a window of ± 14 days. Long-term follow up may be discontinued once the primary end point is assessed and met.

c. If female of childbearing potential, a pregnancy test will be required at screening visit and prior to the start of each cycle of study drug.

d. Laboratory Assessments:

- Hematology labs to include hemoglobin, hematocrit, red blood cell count, white blood cell count, platelets (direct platelet count), as well as total and differential CBC counts. The CBC differential includes enumeration of neutrophils, lymphocytes, eosinophils, monocytes, basophils and any abnormal blood cells noted in the differential.

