#### **Non-serious Adverse Event Collection and Reporting**

The collection of non-serious AE information must begin at initiation of study drug. All non-serious adverse events (not only those deemed to be treatment-related) must be collected continuously during the treatment period and for a minimum of 30 days following the last dose of study treatment.

Non-serious AEs must be followed to resolution or stabilization, or reported as SAEs if they become serious. Follow-up is also required for non-serious AEs that cause interruption or discontinuation of study drug and for those present at the end of study treatment as appropriate.

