### 8.5.3. SKCC Reporting SAEs to BMS

All Serious Adverse Events (SAEs) that occur following the subject's initiation of study treatment, unless AE/SAE is caused by a study specific screening procedure, through 30\* days of discontinuation of dosing must be reported to BMS Worldwide Safety, whether related or not related to study drug. If applicable, SAEs must be collected that relate to any later protocol-specified procedure (eg, a follow-up skin biopsy).

Following the subject's initiation of treatment, unless AE/SAE is caused by a study specific screening procedure, all SAEs, whether related or not related to study drug, are collected, including those thought to be associated with protocol-specified procedures. The investigator must report any SAE occurring after these aforementioned time periods, which is believed to be related to study drug or protocol-specified procedure.

An SAE report must be completed for any event where doubt exists regarding its seriousness;

If the investigator believes that an SAE is not related to study drug, but is potentially related to the conditions of the study (such as withdrawal of previous therapy or a complication of a study procedure), the relationship must be specified in the narrative section of the SAE Report Form.

If the BMS safety address is not included in the protocol document (eg, multicenter studies where events are reported centrally), the procedure for safety reporting must be reviewed/approved by the BMS Protocol Manager. Procedures for such reporting must be reviewed and approved by BMS prior to study activation.

An appropriate SAE form (e.g. ex-US = CIOMS form or USA = Medwatch form) must be used to report SAEs to BMS. The BMS protocol ID number must be included on whatever form is submitted by the Sponsor/Investigator.

- The CIOMS form is available at: <http://www.cioms.ch/index.php/cioms-form-i>
- The MedWatch form is available at:  
<https://www.fda.gov/downloads/AboutFDA/ReportsManualsForms/Forms/UCM048334.pdf>

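### The 30-day limit on adverse event reporting conflicts with the protocol's own statement on late immune-related events, and leaves late non-serious ones without a clear recording rule

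*Combined protocol and SAP*

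**What the plan says.** Section 8.3 (Safety Assessment and Follow-Up) has AE reporting "continue until 30 days after the last dose of study treatment". Its next sentence sets no end date: "At each study visit, the investigator (or designee) will inquire about the occurrence of AE/SAEs since the last visit". It then adds: "Events will be followed for outcome information until resolution or stabilization".

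Four other places bear on the same window:

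- Section 5.7, on immune-related events: "An irAE can occur shortly after the first dose or several months after the last dose of treatment".
- Table 3 (Section 6.1), AE Assessment row: "Assessed at every visit". The schedule in that table runs to month 48.
- Section 8.4.5, under Non-serious Adverse Event Collection and Reporting: collection runs through treatment and "for a minimum of 30 days following the last dose of study treatment".
- Section 8.5.3, on SAEs: those within 30 days "of discontinuation of dosing must be reported to BMS Worldwide Safety, whether related or not related to study drug". For later events: "The investigator must report any SAE occurring after these aforementioned time periods, which is believed to be related to study drug", or to a protocol-specified procedure.

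Section 2.3 makes safety and toxicity, graded by CTCAE version 5.0, a secondary endpoint. Section 9 does not say which period the toxicity analysis covers.

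**The concern.** The limit in Section 8.3 closes AE reporting before the time at which, on the protocol's own account, some drug toxicity can first appear. A site that finds a new, non-serious immune event at month 3 or month 6 cannot tell from the text whether to record it. Section 8.3 read as a limit says no. Section 8.4.5 allows it without requiring it. The visit inquiry and Table 3 suggest yes.

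Two consequences follow. Events left out can only lower the toxicity rate. And sites that read the sections differently will produce data that do not mean the same thing when pooled. Both matter in a population where Section 7.1 says that nearly 70% are cured by excision alone, because toxicity then carries much of the benefit-risk judgement.

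**Working it through.** The plan states no figure for late events, so there is nothing to reproduce. The check compares the sections and then gives the scale.

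**1. Who is covered after day 30**

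- *Events already recorded by day 30:* covered. Section 8.3 follows them to resolution or stabilization. This does not reach new onsets.
- *New SAE, believed related to drug or procedure:* covered by Section 8.5.3, with no time limit.
- *New SAE, judged unrelated:* no clear rule. This matters for toxicity only if the judgement is wrong. Section 8.4.1 makes that possible, since its criteria include a temporal relationship and abatement when the drug is stopped. An event that starts months after the last dose fits both poorly.
- *New non-serious irAE:* no clear rule. Section 8.3 closes reporting, Section 8.4.5 sets only a floor, and the visit inquiry does not say what must be recorded.

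The start of the clock also differs: the last dose in Sections 8.3 and 8.4.5, discontinuation of dosing in Section 8.5.3.

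**2. Calendar**

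Inputs: 12 doses every 4 weeks (Section 3.4); 48 months of follow-up (Section 3.5); visits at M1, M3, M6, M9, M12, M18, M24, M30, M36, M42 and M48 (Table 3), taken as counted from the last infusion at 30.44 days per month.

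- Last dose, with the first on day 0: 11 × 28 = day 308.
- End of window: 308 + 30 = day 338.
- M1 is about 30 days after the last dose, on the edge of the window. M3 is at about 91 days; with the 6-week allowance in note k of Table 3, the earliest is 91 − 42 = 49 days, still outside.
- So 10 of 11 follow-up visits fall after the window.
- Share of follow-up inside the window: 30 / (48 × 30.44) = 30 / 1,461 = 2.1%.

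**3. Scale**

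Inputs: n = 63 evaluable and 73 enrolled (Section 9.3). The proportion p with a first irAE after day 30 is an assumption, shown from 1% to 10%.

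Expected patients = n × p; chance of at least one = 1 − (1 − p)^n.

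| p (assumed) | n = 63: expected | n = 63: at least one | n = 73: expected | n = 73: at least one |
|---|---|---|---|---|
| 1% | 0.6 | 47% | 0.7 | 52% |
| 2% | 1.3 | 72% | 1.5 | 77% |
| 5% | 3.2 | 96% | 3.7 | 98% |
| 10% | 6.3 | 99.9% | 7.3 | >99.9% |

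Each missed patient moves a rate by 1/73 = 1.4 to 1/63 = 1.6 percentage points.

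For any given p, these counts are upper bounds on the patients missed. They include late irAEs that are serious and judged related, which Section 8.5.3 captures, and any that a site records because of the visit inquiry.

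**The case against.** The best defence is that the protocol does not in fact stop looking at day 30. Investigators ask about AEs at each visit. Table 3 keeps history, examination and laboratory tests in follow-up, and the listed tests include TSH, ALT, AST, bilirubin, creatinine and glucose. Section 8.4.5 permits later collection. Section 8.2.3 counts important medical events as serious, so a late immune event of that kind, if believed related, remains reportable. All of this stands, and it narrows the gap. It does not close it: seeing an abnormality is different from being required to record it as an AE, and Section 8.3 read literally says that reporting is over.

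A reader might infer more than the text supports in four ways:

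- *That late toxicity as a whole is lost.* Section 8.5.3 and the visit inquiry rule this out.
- *That every late SAE judged unrelated is missed toxicity.* If the judgement is right, it is not drug toxicity.
- *That patients who stop early for toxicity are specially disadvantaged.* The window in Section 8.3 has the same length from each patient's own last dose. The event that caused stopping is followed under Sections 8.3 and 8.4.5. Only a new event is exposed, as for anyone else.
- *That a definite number of patients will be missed, for example 3 to 7.* That rests on an assumed 5% to 10% rate, and is an upper bound even then.

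There are also limits on the reading. The Table 3 text is broken, so the columns that the AE row spans cannot be confirmed; Section 8.3 requires the inquiry independently. The 30 in Section 8.5.3 carries an asterisk whose footnote is not visible.

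**Conclusion.** The point holds in a narrow form. The 30-day limit in Section 8.3 is inconsistent with Section 5.7, with its own visit inquiry and with Section 8.4.5, and apparently with Table 3. As written, late-onset non-serious irAEs, and late SAEs misjudged as unrelated, can be left out of the toxicity endpoint or handled differently by site. Any error from omission is downward.

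The size is not known from the documents. Across the assumed 1% to 10%, at most 0.6 to 7.3 patients would be affected. The conclusion that the sections must be reconciled does not depend on that rate; only the practical importance does. This bears on a secondary endpoint and leaves the primary recurrence-free survival analysis untouched.

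**What to change.** - Reconcile Section 8.3, Section 8.4.5, Section 8.5.3 and the AE row of Table 3. State one end date each for non-serious AEs, irAEs and SAEs, all counted from the same defined starting point.
- After day 30, record new-onset irAEs of any grade, and SAEs whatever their attribution, at the follow-up visits already scheduled. If other non-serious AEs stop at day 30, say so in the Table 3 row.
- In Section 9, state the period that the toxicity analysis covers, and report late-onset events on a separate line.
- Note m of Table 3 and Section 7.1 follow patients who stop for progression for survival only. State that their late irAEs are not captured. Note e, which has visits resume after discontinuation for any reason including progression, should be reconciled with note m at the same time.

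The cost is protocol wording and some extra data entry, with no new visits or tests. The reported toxicity rate may rise. A separate line for late events keeps the rate up to day 30 available for comparison with studies that use that window.

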### **8.4. Recording Adverse Events**

The following subsections detail what information must be documented for each adverse event.

#### **8.4.1. Relationship to Study Intervention**

The relationship to study intervention or study participation must be assessed and documented for all adverse events. Evaluation of relatedness must consider etiologies such as natural history of the underlying disease, concurrent illness, concomitant therapy, study-related procedures, accidents, and other external factors.

The following guidelines are used to assess relationship of an event to study intervention:

1. Related (Possible, Probable, Definite)

- a. The event is known to occur with the study intervention.
  - b. There is a temporal relationship between the intervention and event onset.
  - c. The event abates when the intervention is discontinued.
  - d. The event reappears upon a re-challenge with the intervention.
2. Not Related (Unlikely, Not Related)
- a. There is no temporal relationship between the intervention and event onset.
  - b. An alternate etiology has been established.

#### **8.4.2. Expectedness**

The PI is responsible for determining whether an AE is expected or unexpected. An AE will be considered unexpected if the nature, severity, or frequency of the event is not consistent with the risk information previously described for the intervention. Risk information to assess expectedness can be obtained from preclinical studies, the investigator's brochure, published medical literature, the protocol, or the informed consent document.

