#### **8.5.1.3. Serious Adverse Events**

SAEs will be reported to the IRB.

Grade 3-4 AEs that are unexpected and deemed to be at least possibly related to the study will be reported to the IRB within 2 working days of knowledge of the event.

Grade 3-4 AEs that are deemed unrelated to the study will be reported to the IRB within 5 working days.

Grade 5 AEs will be reported to the IRB within one working day of knowledge of the event.

All SAEs will be submitted to the IRB at continuing review, including those that were reported previously.

SAEs occurring at the sub-site are to be reported to the sub-site IRB per institutional guidelines. Section 8.5.1.4 provides information on reporting SAEs to TJU.

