#### **8.5.1.4 Sub-Site SAE Reporting**

All SAEs occurring at the sub-site must be reported to the TJU Study Site Contact within 24 hours of notification. This initial notification can take place via email or phone, followed by the submission of a formal report.

SAEs must be reported to TJU using the FDA Medwatch 3500A, and must comprise a full written summary, detailing relevant aspects of the adverse events in questions, including grading and attribution to study drug. Where applicable, information from relevant hospital case records and autopsy reports must be included.

SAE Reports must be signed by the sub-site PI, and then emailed to the Thomas Jefferson University Study Site Contact within 24 hours.

The TJU coordinator will notify the TJU PI and obtain the TJU PI signature, and report these events to the TJU Medical Monitor/IRB appropriately (within 5 working days if it deems an amendment, or in a spreadsheet at the time of annual review if no amendment is necessary).

Additional follow-up SAE reports must be submitted when available.

All reportable Adverse Events (AEs) must be reported to the TJU Research Coordinator within 48 hours using the FDA MedWatch 3500 form.

A reportable AE is any adverse event NOT identified in the IB or consent form as a risk.

Any non-reportable AE must be kept by the sub-site on an ongoing tracking log to be reviewed by TJU quarterly.

Unanticipated problems (UAPs) that pose risk to subjects or others, and that are not AEs/SAEs should be reported to TJU within 5 working days using form Unanticipated Problems Form (see Appendix 2) and must be emailed to the TJU Study Site Contact within 5 business days.

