The sponsor will reconcile the clinical database SAE cases (case level only) transmitted to BMS Global Pharmacovigilance ([[contact]](mailto:[contact])). Frequency of reconciliation must be every 3 months and prior to the database lock or final data summary. GMS GPV&E will email, upon request from the Investigator, the GPV&E reconciliation report. Requests for reconciliation must be sent to [[contact]](mailto:[contact]). The data elements listed on the GPV&E reconciliation report will be used for case identification purposes. If the Investigator determines a case was not transmitted to BMS GPV&E, the case must be sent immediately to BMS.

In accordance with local regulations, BMS will notify investigators of all reported SAEs that are suspected (related to the investigational product) and unexpected (ie, not previously described in the IB). An event meeting these criteria is termed a Suspected, Unexpected Serious Adverse Reaction (SUSAR). Investigator notification of these events will be in the form of a SUSAR Report.

- Other important findings which may be reported by BMS as an Expedited Safety Report (ESR)

include: increased frequency of a clinically significant expected SAE, an SAE considered associated with study procedures that could modify the conduct of the study, lack of efficacy that poses significant hazard to study subjects, clinically significant safety finding from a nonclinical (eg, animal) study, important safety recommendations from a study data monitoring committee, or sponsor decision to end or temporarily halt a clinical study for safety reasons.

- Upon receiving an ESR from BMS, the investigator must review and retain the ESR with the IB. Where required by local regulations or when there is a central IRB/IEC for the study, the sponsor will submit the ESR to the appropriate IRB/IEC. The investigator and IRB/IEC will determine if the informed consent requires revision. The investigator must also comply with the IRB/IEC procedures for reporting any other safety information.
- In addition to the Sponsor Investigator's responsibility to report events to their local HA, suspected serious adverse reactions (whether expected or unexpected) shall be reported by BMS to the relevant competent health authorities in all concerned countries according to local regulations (either as expedited and/or in aggregate reports).

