#### **8.5.4 SKCC Reporting to the FDA**

For studies conducted under an Investigator IND in the US, any event that is both serious and unexpected must be reported to the Food and Drug Administration (FDA) as soon as possible and no later than 7 days (for a death or life-threatening event) or 15 days (for all other SAEs) after the investigator's or institution's initial receipt of the information. BMS will be provided with a simultaneous copy of all adverse events filed with the FDA.

SAEs must be reported on MedWatch Form 3500A, which can be accessed at:

<http://www.accessdata.fda.gov/scripts/medwatch/>.

MedWatch SAE forms must be sent to the FDA at:

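### Expectedness is judged against four different references, so a related Grade 3-4 event absent from the Investigator's Brochure can miss the 2-working-day IRB report and, if serious, the investigator's own FDA report

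*Combined protocol and SAP*

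**What the plan says.** Section 8.4.2 names who decides: "The PI is responsible for determining whether an AE is expected or unexpected". An event is unexpected if its nature, severity or frequency does not fit the risk already described for the intervention. On sources, the section says: "Risk information to assess expectedness can be obtained from preclinical studies, the investigator's brochure, published medical literature, the protocol, or the informed consent document". It states no order of precedence.

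Three other sections set a different reference:

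- 8.5.1.4, for sub-sites: "A reportable AE is any adverse event NOT identified in the IB or consent form as a risk". Such events go to the lead site within 48 hours. All other non-serious events stay on a sub-site log that the lead site reviews quarterly.
- 8.5.3, for the supplier's SUSARs: "unexpected (ie, not previously described in the IB".
- 8.2.1, for unanticipated problems: risk as "described in the protocol-related documents, such as the IRB-approved research protocol and informed consent document".

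The main rules that turn on the term are these:

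- 8.5.1.3 sets a 2-working-day IRB report for "Grade 3-4 AEs that are unexpected and deemed to be at least possibly related to the study".
- 8.5.4 says that "any event that is both serious and unexpected must be reported to the Food and Drug Administration (FDA) as soon as possible", with a limit of 7 days for fatal or life-threatening events and 15 days for other SAEs. It names no reference document.
- The 8.5.2 table has separate expected and unexpected columns for DSMC reporting at Grades 2 and 3.

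**The concern.** Expectedness decides which events receive an expedited report. If the person who applies the term may draw on a wider body of risk information than the other parties use, the same event can be expected at one desk and unexpected at the next. The widest list is the PI's, and the PI's judgement governs the investigator's IRB and FDA clocks. A new serious immune-mediated reaction with some published or preclinical description, but no entry in the IB, is the case most exposed.

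The sub-site rule has the opposite weakness. It asks only whether an event is named as a risk, whereas 8.4.2 also counts severity and frequency. The Synopsis lists five centers, one of which is the lead site, so four centers report through this rule.

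**Working it through.** No arithmetic applies. The check sets the definitions side by side and follows two events through the reporting rules.

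| Section | Used for | Reference | Severity and frequency counted? |
|---|---|---|---|
| 8.4.2 | PI's judgement | Preclinical studies, IB, literature, protocol, consent form | Yes |
| 8.5.1.4 | Sub-site reportable events | IB or consent form | No |
| 8.5.3 | Supplier's SUSARs | IB | Not stated |
| 8.2.1 | Unanticipated problems | Protocol-related documents, with protocol and consent form as examples | Yes |

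**Event 1: serious, related, Grade 3-4, at the lead site; described in the literature, absent from the IB and consent form.** Section 8.4.2 permits expected. Section 8.5.3 makes it unexpected. If the PI calls it expected:

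- *IRB.* The 2-working-day rule is not triggered. Section 8.5.1.3 gives no other deadline for related Grade 3-4 events, so continuing review remains. With the annual renewal mentioned in 8.1, that is up to about 12 months.
- *FDA.* The rule in 8.5.4 needs both seriousness and unexpectedness. Because it names no reference, 8.4.2 supplies one, and the 7- or 15-day report is not triggered. This rule has no grade condition. The sub-site form in 8.5.4 for fatal or life-threatening, possibly related events also depends on the word unexpected.
- *DSMC.* For related Grade 3 without hospitalization, the phase II entry moves from 5 working days to the quarterly meeting. No other contrast in the table changes: related Grade 3 with hospitalization is 48 hours in both columns (24 hours for a death), unrelated Grade 3 is the same in both, and Grades 4 and 5 are pooled.

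**Event 2: non-serious, related Grade 3, no hospitalization, at a sub-site; named in the IB but more severe than described there.** Under 8.4.2 it is unexpected. Section 8.5.1.3 then asks for an IRB report in 2 working days, and 8.5.2 for a DSMC report in 5. Under 8.5.1.4 it is identified as a risk, so it is not reportable and goes on the quarterly log. The 24-hour sub-site notice covers SAEs only and does not catch it. The lead site may learn of it after both deadlines.

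**Rules that do not depend on expectedness:**

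- IRB report of Grade 5 events: 1 working day (8.5.1.3).
- IRB report of unrelated Grade 3-4 events: 5 working days (8.5.1.3).
- Sub-site SAE notice to the lead site: 24 hours (8.5.1.4).
- Lead-site IRB timing for sub-site SAEs, which depends on whether an amendment is needed (8.5.1.4).
- SAE notice to the supplier: 24 hours (8.5.3).
- The supplier's reports of suspected serious reactions to authorities, expected or not (8.5.3).

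**The case against.** The best case against the point is that the safety net is wider than two clocks. Every SAE reaches the supplier within 24 hours. The supplier classifies it against the IB, sends SUSAR reports to investigators, and reports suspected serious reactions to health authorities. A reader might infer that the IRB and FDA would never hear of such an event, or that serious events in general lose expedited reporting. The documents do not support either reading. Fatal events and unrelated Grade 3-4 events keep their IRB deadlines, all SAEs reach the IRB at continuing review, and the supplier's route to authorities stays open. That route does not close the gap, however. Section 8.5.3 allows it to be expedited or aggregate, and describes it as additional to the sponsor-investigator's own duty.

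A second stronger reading is that one case report makes an event expected. Section 8.4.2 says that sources can be used, not that they must be, and the event must still fit the described nature, severity and frequency. This stands as a limit on the claim. The section nevertheless sets no threshold for what counts as described, so it does not exclude a lenient call.

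Third, the rule in 8.5.1.4 governs transmission to the lead site and is not labelled a definition of expectedness. Serious events bypass it, and 8.1 assigns a medical monitor to day-to-day review. This narrows the sub-site gap to non-serious events. The monitor can act only on what has been reported, and these events are on a log.

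Finally, the IB is not among the documents, so no actual event can be shown to fall in the gap. That limits what can be said about frequency. It does not remove the conflict in wording.

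**Conclusion.** The point holds as a safety-reporting inconsistency with defined limits. Under the PI's broad list, a related Grade 3-4 event absent from the IB can move:

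- from 2 working days to continuing review at the IRB;
- if serious, from 7 or 15 days to no expedited investigator report at the FDA;
- for related Grade 3 without hospitalization, from 5 working days to the quarterly meeting at the DSMC.

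Separately, a listed, non-serious, related Grade 3 event of unexpected severity at a sub-site can wait for a quarterly log review.

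This rests on four assumptions:

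- The PI uses the latitude that 8.4.2 gives.
- The trial runs under an investigator IND, which is the condition in 8.5.4; 4.5 refers to an IND sponsor.
- The Grade 3-4 rule in 8.5.1.3 covers non-serious events. Its heading names serious events, but its wording says AEs, and 8.5.1.2 covers only Grades 1 and 2.
- The IRB clock starts when the sub-site knows of the event. Section 8.5.1.3 does not say whose knowledge counts.

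How often this would occur cannot be estimated from the documents. The sample size and the primary analysis are not affected.

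**What to change.** In 8.4.2, name one reference for expectedness at all sites: the current IB, judged on nature, severity and frequency. The IB is the natural choice because 8.5.1.4 and 8.5.3 already rely on it. Remove preclinical studies and published literature as grounds for calling an event expected.

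Make 8.5.1.3, 8.5.1.4, 8.5.2 and 8.5.4 refer to that definition. In 8.5.1.4 it should replace the test of whether the event is merely named as a risk. Reconcile 8.2.1 with it as well; otherwise a second reference remains for unanticipated problems.

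The cost is a few sentences of protocol wording and probably a few more expedited reports.
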